3 CLINICAL STUDY DETAILS

3.1 Clinical Study Objectives

3.1.1 Primary objective

To assess the safety and tolerability of CM4620-IE in patients with acute pancreatitis and accompanying SIRS

3.1.2 Primary endpoint

The primary endpoints of the study are related to safety, these include Adverse Events (AEs), Vital Signs (VS) and safety laboratory measures

3.1.3 Secondary objectives

To assess the efficacy of CM4620-IE in patients with acute pancreatitis and accompanying SIRS

To determine the pharmacokinetic profile of CM4620-IE in patients with acute pancreatitis and accompanying SIRS

3.1.4 Secondary endpoints

The secondary efficacy endpoints are:

- CTSI Score categorized into Mild, Moderate and Severe
- Balthazar score
- Pancreatic Parenchymal Necrosis
 - < 30%
 - 30-50%
 - > 50%
- PASS score
- Tolerating Solid Food
 - Time to tolerating solid food
 - Arithmetic mean of time to tolerate 50% solid food
- Biomarker measurements including, but not limited to:
 - ANC/ALC (Absolute neutrophils count / Absolute Lymphocytes count)
 - C-Reactive Protein (CRP)
 - D-Dimer

- Procalcitonin
- IL-6
- IL-8
- SIRS
 - Time to resolution of SIRS
 - The number of days alive and free from SIRS
 - Total SIRS score
- Any Organ Failure (LISTINGS)
- Respiratory Failure (LISTINGS)
- Renal Failure (LISTINGS)
- Cardiovascular Failure (LISTINGS)
- Sequential Organ Failure Assessment (SOFA):
 - Respiration Score
 - Coagulation Score
 - Liver Score
 - Cardiovascular Score
 - Central Nervous System Score
 - Renal Score
 - SOFA total Score
- Modified Sequential Organ Failure Assessment (MSOFA):
 - Modified total SOFA Score
- Severity as defined by Revised Atlantic Classification of Acute Pancreatitis
- Severity as defined by Determinant Based Classification of Acute Pancreatitis
- APACHE II score
- Pain Numeric Rating Scale (PNRS) score
- Critical-Care Pain Observation Tool (CPOT) score
- Overall Survival (Listings)
- Number of hospitalized days
 - Total Days
 - Days in Intensive Care

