For all 4 cohorts, a study physician or appropriately trained delegate will perform all assessments daily through Day 10, or until discharge if occurring earlier. After Day 10, and starting on Day 12, serious adverse events (SAEs) will be captured every 48 hours until Day 30 (\pm 2 days), or until discharge if occurring earlier. Patients discharged prior to Day 30 will be contacted on Day 30 (\pm 2 days) to capture SAEs and any re-admissions to the hospital. Patients will also be contacted on Day 90 (\pm 7 days) to assess mortality.

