4.5 Summary Statistics

In general, all data collected will be presented with summary statistics and given in patient data listings. Summary statistics will include at least number of patients, mean, standard deviation, median, minimum and maximum for continuous data and frequency and percentage for categorical data. Table with summary statistics will be divided by treatment group and dose group, and visit where applicable. Patient data listings will be sorted by treatment, subject and timing of assessments.

For confidence intervals for proportions will the Clopper-Pearson exact formula be used.

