4.8 Handling of Drop-outs, Missing Data and Outliers

Outliers will be included in summary tables and listings, and will not be handled separately in any analyses. No imputation of missing data will be performed (however, will data entered in unscheduled visit be placed to the nearest applicable visit with missing values).

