7.4 Secondary Endpoints – Solid food

7.4.1 Definition

The definition of tolerating solid food is that at least 50% is tolerated. Then will the time to first occurrence of tolerating solid food be calculated as date of tolerating solid food – date of randomization +1.

At each visit will tolerating solid food be coded into yes or no.

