7.4.2 Analysis

No analyses will be performed

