7.4.3 Presentation

The variable tolerating food as yes/no will be presented using frequency tables.

The variable tolerating food as percentage will be presented using summary statistics.

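### Time to solid food is summarised as an arithmetic mean with no rule for patients who never reach it, so failures and deaths drop out and delay is understated in the arm with more of them

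*SAP*

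**What the plan says.** SAP 3.1.4 lists two items under tolerating solid food: the time itself, and "Arithmetic mean of time to tolerate 50% solid food".

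SAP 7.4.1 sets the threshold: "The definition of tolerating solid food is that at least 50% is tolerated". It then defines the variable: "Then will the time to first occurrence of tolerating solid food be calculated as date of tolerating solid food", minus the randomization date, plus 1. It also codes tolerance as yes or no at each visit.

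SAP 7.4.2 states "No analyses will be performed". SAP 7.4.3 covers two presentations, neither of them the time variable: "The variable tolerating food as yes/no will be presented using frequency tables", and a summary of the percentage tolerated.

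The general rules also apply. SAP 4.8: "No imputation of missing data will be performed". SAP 4.5: "Summary statistics will include at least number of patients, mean, standard deviation, median, minimum and maximum for continuous data".

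On observation, SAP 3.2 has staff "perform all assessments daily through Day 10, or until discharge if occurring earlier". Protocol 8.11.5 records solid food intake with the vital signs, which the schedule of events carries to Day 10.

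Other duration endpoints do have end rules. SAP 7.13.1 defines censoring for survival. SAP 7.14.1 sets hospital or ICU time to 30 days when no end is recorded and uses the date of death for patients who die there. Time to solid food has no such rule.

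**The concern.** A time that needs an event date exists only for patients who have the event. With no imputation, no censoring rule and no rule for death, the mean can be taken only over patients who succeeded. Those left out are mainly the ones still not eating at Day 10 and the ones who died, which are the worst outcomes on this endpoint. The more slow patients an arm loses this way, the shorter its mean becomes.

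Protocol 1.6 says the design will allow a dose-response analysis of efficacy as well as safety. No inferential test is planned, so readers will judge efficacy from the descriptive figures. A mean conditional on success, set beside another mean conditional on a different success rate, does not compare the randomized groups. The error can favour either side: it flatters whichever arm has more failures.

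**Working it through.** **Arm sizes.** Cohorts of 4 + 4 + 8 + 8 give 24, matching SAP 3.3 and 4.2. At 3:1 this is 24 × 3/4 = 18 on CM4620-IE and 24 × 1/4 = 6 on supportive care alone. One non-reacher is 1/6 (17%) of the control arm. The plan gives no tolerance rate, death rate or power calculation, so there is no further figure to reproduce.

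**Denominator.** The SAP does not say in words that the mean is over reachers. It follows from 7.4.1 (time = tolerance date − randomization date + 1, undefined without a tolerance date) together with 4.8. No other text supplies a value.

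**Illustration (assumed days).** The 6 controls tolerate food on Days 3, 4, 5, 6, 7 and 8: 33/6 = 5.5. The 18 treated patients have three on each of those days (sum 99), except that the slowest k never reach the endpoint. Day 11 is the first day after the observation window and is used only as a floor for non-reachers.

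| k | Mean over reachers | Non-reachers at Day 11 | Proportion reaching |
|---|---|---|---|
| 1 | (99 − 8)/17 = 5.35 | (91 + 11)/18 = 5.67 | 17/18 = 94% |
| 3 | (99 − 24)/15 = 5.00 | (75 + 33)/18 = 6.00 | 15/18 = 83% |
| 6 | (99 − 24 − 21)/12 = 4.50 | (54 + 66)/18 = 6.67 | 12/18 = 67% |

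The treated arm is worse in every row, yet its mean over reachers is 0.15, 0.50 or 1.00 day shorter than the control mean of 5.5. The median with non-reachers ranked last is the midpoint of the 9th and 10th values, (5 + 6)/2 = 5.5, for every k from 1 to 6. A median alone would also miss these failures.

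**Simulation (assumed hazards).** There were 20,000 trials per scenario, 18 treated and 6 controls, exponential times rounded up to whole days and a 10-day window. The control tolerance hazard was 0.2/day with no control deaths. Entries are treated minus control mean days; a positive value means the treated arm is slower.

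| Tolerance hazard ratio | Treated death hazard per day | Difference, reachers only | Difference, non-reachers at Day 11 | Trials where treated looks faster: reachers only / all patients |
|---|---|---|---|---|
| 0.7 | 0 | +0.43 | +1.12 | 36% / 24% |
| 0.7 | 0.05 | +0.06 | +1.70 | 46% / 15% |
| 0.5 | 0.10 | +0.01 | +3.05 | 49% / 4% |
| 0.7 | 0.10 | −0.27 | +2.23 | 56% / 10% |

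In all four scenarios the reachers' mean understates the disadvantage. Only the last reverses it on average. That scenario assumes no control deaths and treated deaths before tolerance by Day 10 of 0.10/0.24 × (1 − e^−2.4) ≈ 38%.

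**The case against.** The strongest reply is that failures remain visible elsewhere. SAP 4.5 requires n, median and range beside the mean, together with patient listings, so n against arm size shows how many patients lack a time. The yes/no table in 7.4.3 shows tolerance by visit. PASS (7.3) adds 40 points for not tolerating a solid diet, and deaths are listed (7.13.3). This stands in part: a reader should not infer that the worst outcomes vanish from the report. But none of these items changes the mean, and a by-visit table is not a cumulative proportion of all randomized patients.

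A reader might also infer that the worse arm will look faster. The documents do not support that. They give no event rates, and average reversal in the simulation needed an extreme difference in deaths. With 1 of 18 treated patients missing, the shift in the illustration is 0.15 day. Understated delay is the usual effect; reversal is possible.

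Finally, the endpoint is one of many secondary items, no test is planned, the primary endpoint is safety, and the trial is not powered. That is correct and limits the severity. It does not justify a summary that improves when slow patients fail.

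**Conclusion.** The point holds. Followed as written, the SAP averages time to solid food over successes only, with no provision for patients who do not tolerate food by Day 10 or who die first. This understates delay in an arm with more failures and could reverse the comparison if failures differ enough. In the illustration the understatement is 5.67 − 5.35 = 0.32, 6.00 − 5.00 = 1.00 or 6.67 − 4.50 = 2.17 days for 1, 3 or 6 non-reachers of 18.

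These sizes rest on assumed event days, on the slowest patients being the ones who fail, and on Day 11 as a floor. If failures were unrelated to speed, the reachers' mean would on average stay at 5.5 and simply not register them. The missing rule is certain from the text; the size of its effect is not known. The priority is low to moderate, given one descriptive secondary endpoint in 24 patients.

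**What to change.** In SAP 7.4:

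- Report by arm, with all randomized patients as the denominator, the number and cumulative proportion first tolerating solid food by Day 5 and by Day 10, and the cumulative incidence curve to Day 10.
- Treat death before tolerance as a competing event, so that the patient stays in the denominator as never tolerating.
- Censor patients who are alive and not tolerating at their last food assessment. List those discharged before tolerating, and add a sensitivity analysis counting them as not tolerating. Tolerating a normal diet is a suggested discharge criterion (Protocol 5.2), so censoring at discharge may be informative.
- Give the median with non-reachers ranked last only beside these proportions.
- If the arithmetic mean is kept, label it as conditional on reaching the endpoint and show n reached / n randomized.
- Add the time variable to 7.4.3.

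The cost is SAP wording, one changed table and slightly more analysis work. The food data are already collected under Protocol 8.11.5, and SAP section 2 requires sign-off only before database lock.

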3.2 Clinical Study Design

This open-label, dose-response study will evaluate the safety and efficacy of CM4620-IE in patients with acute pancreatitis and accompanying SIRS. The study will consist of two phases. The first phase will consist of 2 cohorts that will be enrolled concurrently. Cohort 1 will consist of 4 female patients who will be randomized 3:1 to receive CM4620-IE plus supportive care versus supportive care alone. Cohort 2 will consist of 4 male patients who will be randomized

3:1 to receive CM4620-IE plus supportive care versus supportive care alone. Planned doses for patients in both cohorts who are randomized to receive CM4620-IE are 1.0 mg/kg on Day 1 and 1.4 mg/kg on Days 2-4. The first infusion of CM4620-IE must be started within 6 (up to 8) hours of the patient or LAR providing informed consent and should be administered IV over 4 hours. Subsequent infusions will be started every 24 hours (\pm 1 hour) from the start of the first infusion.

The second phase will consist of 2 cohorts. Cohort 3 will consist of 8 female patients who will be randomized 3:1 to receive CM4620-IE plus supportive care versus supportive care alone. Cohort 4 will consist of 8 male patients who will be randomized 3:1 to receive CM4620-IE plus supportive care versus supportive care alone. Planned doses for patients in both cohorts who are randomized to receive CM4620-IE are 2.08 mg/kg of CM4620-IE on Days 1 and 2, and 1.6 mg/kg on Days 3 and 4. The first infusion of CM4620-IE must be started within 6 (up to 8) hours of the patient or LAR providing informed consent and will be administered intravenously IV over 4 hours. Subsequent infusions will be started every 24 hours (\pm 1 hour) from the start of the first infusion.

The decision to start Cohort 3 will be made after CalciMedica reviews the available efficacy, safety and tolerability data from Cohort 1 and discusses with the Principal Investigators. The decision to start Cohort 4 in the second phase of the study will be made after CalciMedica reviews the available efficacy, safety and tolerability data from Cohort 2 and discusses with the Principal Investigators.

For all 4 cohorts, a study physician or appropriately trained delegate will perform all assessments daily through Day 10, or until discharge if occurring earlier. After Day 10, and starting on Day 12, serious adverse events (SAEs) will be captured every 48 hours until Day 30 (\pm 2 days), or until discharge if occurring earlier. Patients discharged prior to Day 30 will be contacted on Day 30 (\pm 2 days) to capture SAEs and any re-admissions to the hospital. Patients will also be contacted on Day 90 (\pm 7 days) to assess mortality.

3.3 Number of Subjects

24 randomized subjects

3.4 Methods of Assigning Subject to IMP

Patients will be randomized 3:1 to receive CM4620-IE in addition to supportive care consistent with the [2013 IAP/APA](#) evidence-based guidelines for the management of acute pancreatitis versus supportive care alone. Randomization will be stratified by sex. CalciMedica or its designee will prepare the randomization schedule prior to the start of the study

3.5 Blinding

Not applicable

4 STATISTICAL AND ANALYTICAL PLANS

4.1 General

All endpoints below will be presented by:

- 1) All cohorts

If there will be some exploratory hypothesis testing performed a 5% significance level will be used.

4.2 Sample Size Justification

This open-label study will enroll 24 patients. The sample size was selected based on practical considerations to initially evaluate the safety, efficacy and pharmacokinetic profile of CM4620-IE in patients with acute pancreatitis and accompanying SIRS. This study is not powered for analysis of study data with inferential statistics

4.3 Definition of Analysis Sets

4.3.1 Full Analysis Set

The **Full Analysis Set** (FAS) consists of all randomized patients who receive any amount of CM4620-IE or supportive care. Patients will be analyzed according to treatment they actually received.

4.3.2 Per Protocol Set

No Per Protocol Set will be used.

4.4 Definition of Baseline

Baseline measurement is defined as the latest measurement prior to first dose of IMP including Apache II score.

4.5 Summary Statistics

In general, all data collected will be presented with summary statistics and given in patient data listings. Summary statistics will include at least number of patients, mean, standard deviation, median, minimum and maximum for continuous data and frequency and percentage for categorical data. Table with summary statistics will be divided by treatment group and dose group, and visit where applicable. Patient data listings will be sorted by treatment, subject and timing of assessments.

For confidence intervals for proportions will the Clopper-Pearson exact formula be used.

4.6 Significance Level

If applicable will 5% significance level be used.

4.7 Multiple Comparisons/Multiplicity

No adjustment for multiple comparison/multiplicity will be performed, all significant statistical findings, must be reviewed for medical relevance.

4.8 Handling of Drop-outs, Missing Data and Outliers

Outliers will be included in summary tables and listings, and will not be handled separately in any analyses. No imputation of missing data will be performed (however, will data entered in unscheduled visit be placed to the nearest applicable visit with missing values).

4.9 Adjustment for Covariates

Not applicable

4.10 Multicenter Studies

No adjustment for sites will be performed.

4.11 Examination of Subgroups

Gender and HCT/ALB will be used as subgroups for all secondary endpoints.

4.12 Blind Review

Not applicable.

5 SUBJECTS

5.1 Subject Disposition

The number of subjects that entered the study, withdrawn subjects, completed subjects and the number of subjects at each visit will be summarized by treatment.

5.2 Baseline Characteristics and Demographics

All baseline and demographic data will be presented using summary statistics.

6 TREATMENT INFORMATION AND EXTENT OF EXPOSURE

6.1 Active Treatment

The number of subjects on each IP will be tabulated with start time, stop time and duration of application will be tabulated using listings and summary statistics.

6.2 Prior and Concomitant Medications

Prior and concomitant medication data will be listed and tabulated by ATC code. Prior and concomitant medications will be coded according to the World Health Organization (WHO Drug Dictionary) classification system.

7 STATISTICAL METHODOLOGY

All parameters will be presented by treatment and visit using summary statistics. Additional statistical analyses are specified below.

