For all 4 cohorts, a study physician or appropriately trained delegate will perform all assessments daily through Day 10, or until discharge if occurring earlier. After Day 10, and starting on Day 12, serious adverse events (SAEs) will be captured every 48 hours until Day 30 ( $\pm$  2 days), or until discharge if occurring earlier. Patients discharged prior to Day 30 will be contacted on Day 30 ( $\pm$  2 days) to capture SAEs and any re-admissions to the hospital. Patients will also be contacted on Day 90 ( $\pm$  7 days) to assess mortality.

CalciMedica may submit amendments to the protocol to modify the planned doses, the dosing schedule, the infusion time, the number of sites in the study, the total number of patients randomized in the study, the number of patients randomized in each cohort, the number of cohorts in each phase of the study, and/or the number of phases in the study for safety and/or efficacy considerations.

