### 5.2 Discharge Criteria

The patient randomized to receive CM4620-IE should remain in the hospital until all 4 doses of CM4620-IE have been administered, and a CECT of the pancreas has been performed. The suggested criteria for discharging patients from the hospital are:

- Abdominal pain has resolved
- Normal oral diet is tolerated
- There is no clinical or laboratory evidence of an infection

If the patient is ready to be discharged before all 4 doses of CM4620-IE have been administered or the CECT of the pancreas has been performed, the PI or treating physician should contact the Medical Monitor prior to discharging the patient.

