**All patients will undergo a CECT of the pancreas on Day 5.**

- The CECT will be performed on Days 6 or 7 if unable to be performed on Day 5
- If the PI wishes to discharge a patient randomized to supportive care only before Day 5, a CECT should be performed prior to discharge
- If the PI wishes to delay the CECT beyond Day 7, the Medical Monitor should be contacted

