## **8.7 Days 6 – 9**

For all patients who remain hospitalized, at 120 hours ( $\pm 1$  hour), 144 hours ( $\pm 1$  hour), 168 hours ( $\pm 1$  hour), 192 hours ( $\pm 1$  hour) from the time of randomization:

- Record vital signs
- Record concomitant medications
- Draw a blood sample for CBC, differential and platelets, chemistry profile, serum biomarkers—send to central lab
- Obtain a urine sample for biomarkers—send to central lab
- Record SpO2 and the FiO2 and time performed

- Calculate the Glasgow Coma Scale Score
- Record patient's pain using the PNRS
- Assess pain using the CPOT
- Perform AE/SAE assessment

## 8.8 Day 10

For all patients who remain hospitalized, at 216 hours ( $\pm 1$  hour) from the time of randomization:

- Record vital signs
- Record concomitant medications
- Perform limited physical examination
- Draw a blood sample for CBC, differential and platelets, chemistry profile, serum biomarkers—send to central lab
- Obtain a urine sample for biomarkers—send to central lab
- Record SpO2 and the FiO2 and time performed
- Calculate the Glasgow Coma Scale Score
- If an ABG has already been performed as part of standard of care, record the pH, PaCO2, PaO2, SaO2 and the FiO2 at the time of draw
- Record patient's pain using the PNRS
- Assess pain using the CPOT
- Perform AE/SAE assessment

For patients randomized to receive CM4620-IE:

- Draw a blood sample for PK at 216 hours ( $\pm 1$  hour) from the start of dose administration on Day 1—send to central lab

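### Up to Day 5 (Day 7 if the CECT is late), by-visit means of observed values can favour CM4620-IE with no drug effect, because recovered controls may leave while recovered drug patients are held

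*SAP*

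**What the plan says.** **Who is measured.** Protocol 3.1 has staff "perform all assessments daily through Day 10, or until discharge if occurring earlier". Protocol 8.7 opens its list for Days 6 to 9 with "For all patients who remain hospitalized", and 8.8 does the same for Day 10. Sections 8.3 to 8.6 address all patients on Days 2 to 5, but no visit is provided for a patient who has gone home.

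**Who stays.** Under Protocol 5.2, a patient randomized to CM4620-IE "should remain in the hospital until all 4 doses of CM4620-IE have been administered" and the CECT has been performed. The CECT is due on Day 5, or on Day 6 or 7 if that is not possible. For the other arm, Protocol 8.6 contains the clause "If the PI wishes to discharge a patient randomized to supportive care only before Day 5" and asks only that the CECT be done first. The suggested discharge criteria in 5.2 (no remaining abdominal pain, normal diet tolerated, no infection) are otherwise the same for both arms.

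**What is averaged.** SAP 7 sets the general rule: "All parameters will be presented by treatment and visit using summary statistics". SAP 4.8 adds: "No imputation of missing data will be performed". PASS, biomarkers, PNRS and CPOT also get graphs over time (SAP 7.3.3, 7.5.3, 7.11.3, 7.12.3). No rule covers patients already discharged.

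**The concern.** Leaving hospital depends on the outcome being summarised. Pain and diet are discharge criteria, pain is the PNRS, and both pain and diet enter PASS. If recovery removed patients from both arms alike, the by-visit means would describe a selected group, but the same selection would apply to each arm. Here the selection differs by arm while the drug patients are held: a recovered control can leave the average, whereas a recovered drug patient stays in it with a low score.

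Descriptive tables and graphs are the whole efficacy output of this study. Protocol 1.6 treats the no-drug patients as one of three dose groups for a dose-response reading. A spurious separation between no drug and either dose on Days 3 to 5 could be taken as an early efficacy signal. The two drug doses share the same stay rule, so the comparison between them is not affected in this way.

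**Working it through.** **1. Arm sizes.** The cohorts are 4 + 4 + 8 + 8 = 24, which reproduces the planned total. At 3:1 this gives 3 + 3 + 6 + 6 = 18 drug and 1 + 1 + 2 + 2 = 6 control patients.

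**2. General form.** Let a share f of each arm be recovered with score 0, and let the rest average m. If all drug patients are held, their mean is (1 − f)m. If recovered controls have left, the control mean is m. The gap is f × m with no treatment effect. Assuming m = 4 on the 0–10 pain scale:

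| Controls gone (of 6) | Drug mean | Control mean | Gap |
|---|---|---|---|
| 0 | 4.00 | 4.00 | 0 |
| 1 | 3.33 | 4.00 | 0.67 |
| 2 | 2.67 | 4.00 | 1.33 |
| 3 | 2.00 | 4.00 | 2.00 |

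**3. SIRS illustration.** Day 1 values are taken just before randomization (Protocol 8.2) and Day 5 is at 96 hours (8.6), so there are four daily recovery steps. Assumptions: score 2 on Day 1 and until recovery, 0 after; a proportion p recovers each day in both arms; controls leave the day after recovery; every drug patient is held.

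- Drug mean on Day 5: 2(1 − p)^4.
- Controls still observed on Day 5 are those not recovered by Day 4: (1 − p)^3.
- Control mean on Day 5: 2(1 − p)^4 / (1 − p)^3 = 2(1 − p).

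| p per day | Drug mean | Control mean | Controls observed |
|---|---|---|---|
| 15% | 1.04 | 1.70 | 61% |
| 20% | 0.82 | 1.60 | 51% |
| 25% | 0.63 | 1.50 | 42% |

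**4. Dependence on the stay assumptions (p = 20%).** If recovered controls stay 1, 2 or 3 days longer, the control mean becomes 2 × 0.8^2 = 1.28, 2 × 0.8^3 = 1.02 or 2 × 0.8^4 = 0.82. The last equals the drug mean, because no control has then left by Day 5. If instead half of the drug patients follow the control rule, the drug mean rises to 2 × 0.4096 / (0.5 + 0.5 × 0.512) = 1.08.

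**5. Pain, and the days after the hold.** A simulation of 40,000 trials (18 versus 6) gave both arms one course: pain starting between 5 and 9 and falling linearly to zero. Controls left when pain had resolved, and drug patients left no earlier than Day 5. With median readiness for discharge on Day 3, 4, 5 or 7, 79%, 50%, 28% or 8% of controls had gone before Day 5. The control-minus-drug gap was:

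- Day 4: 0.33, 0.28, 0.17 or 0.05 points.
- Day 5: 0.41, 0.49, 0.42 or 0.20 points.
- Day 6 onward: within 0.02 of zero.

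With median readiness on Day 4 and 30% of drug patients held to Day 7, the gap was 0.35 on Day 6 and 0.44 on Day 7, then about zero. When patients were also averaged after discharge, the gap was 0.00 on every day.

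**6. Day 10.** The statement placed just before Protocol 8.9 has Day 10 procedures done at discharge for patients leaving after Day 5 and before Day 10. Footnote h of Appendix 11 applies this to any discharge before Day 10. The Day 10 column therefore includes discharge assessments, and the two places disagree on which discharged patients contribute.

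**The case against.** The study is small and descriptive, no tests are planned on these endpoints, and SAP 5.1 reports the number of subjects at each visit. The SAP also lists summaries that do not rest on daily inpatient means: time to SIRS resolution, days alive and free from SIRS, and time to solid food. Patient listings show everything. These points limit the harm without removing it. A count per visit shows that patients have gone but does not correct the mean, and SAP 7.6.3 specifies a presentation only for the total SIRS score.

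The stay rule is worded as a recommendation, with contact to the Medical Monitor before an earlier discharge, so some drug patients may leave before Day 5. SIRS is not among the suggested discharge criteria. A control without SIRS who still has pain stays and adds a zero to the control SIRS mean. Both points stand, and both shrink the gap.

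A reader might infer that the tilt persists through Day 10, or that every later column shows only patients too ill to leave. The documents do not support that. After the hold, one set of discharge criteria applies to both arms, and Day 10 takes in discharge assessments. Nor do they establish that the drug mean covers every patient or that the remaining controls are mostly unrecovered; those are assumptions.

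**Conclusion.** The concern holds for the period in which the stay rules differ: up to Day 5, or Day 7 where the CECT is late. With identical courses, any recovered control who leaves while recovered drug patients are held moves the observed daily means in favour of CM4620-IE. After that, no between-arm bias is expected from this rule. Days 6 to 9 simply describe a shrinking inpatient subset in both arms, and Day 10 cannot be interpreted until its two rules are reconciled.

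The direction follows from the text, but the size does not. Under the SIRS assumptions above, the Day 5 gap is 0.66, 0.78 or 0.87 points at 15%, 20% or 25% recovery per day (1.70 − 1.04, 1.60 − 0.82, 1.50 − 0.63). The simulated pain gap on Day 5 is 0.20 to 0.49 points on a 0–10 scale. With six controls, one or two early discharges are enough to change the control curve. The problem affects how tables and graphs are read, not a formal test.

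**What to change.** In SAP 7, add a status table for each of Days 1 to 10, by arm and over all randomized patients: in hospital with SIRS, in hospital without SIRS, discharged alive, died. Make it the between-arm summary of the daily course. It imputes nothing, and the discharge and death dates are already needed for SAP 7.13 and 7.14.

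Label the observed by-visit means and graphs as inpatients only, and state that they are not to be read as a between-arm comparison while the stay rules differ. Reconcile the Day 10 statement before Protocol 8.9 with footnote h of Appendix 11, and say in the SAP which discharge assessments enter the Day 10 column.

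Do not make last value carried forward, with the worst score after death, the main summary for biomarkers or PASS. CRP, D-dimer and IL-6 have no defined worst value, and the morphine term in PASS has no cap. Carrying forward would also keep the tilt: if a marker halves daily, discharge one day earlier doubles the carried value. For bounded scores (SIRS, SOFA, PNRS, CPOT) it could serve as a sensitivity display, with its assumption stated.

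The cost is SAP wording, one extra table and a coarser daily summary. No trial procedure changes.
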